**Table 1 Changes to Protocol Defined Analysis Plan**

Protocol Defined Analysis	SAP Defined Analysis	Rationale for Changes

 
• Exploratory analyses                             
 
○ Biomarker analysis
 
 
 
• Interim analysis for DE phase
 
• All analysis related to CE phase
 
	The listed protocol defined analyses will not be included in this sub-study.	This sub-study was terminated during DE phase due to observed lack of efficacy.

### 1.2. Objectives, Estimands and Endpoints

The primary and secondary objectives, along with the corresponding endpoints for Dose Exploration are listed in Table 2.

**Table 2 Dose Exploration (DE)**

Objectives	Endpoints
Primary	
To determine the safety and tolerability of belantamab mafodotin in combination with aOX40 and to establish the recommended Phase 2 dose for the combination treatment to explore in the CE Phase in participants with RRMM.	
 
• Percentage (number) of participants with dose limiting toxicities (DLTs)
 
• Percent of subjects with AEs, changes in clinical signs and laboratory parameters
 

Key Secondary	

**CONFIDENTIAL**

Objectives	Endpoints
To evaluate the clinical measures of efficacy of belantamab mafodotin and aOX40 in participants with RRMM	
 
Clinical activity measured as Overall Response Rate (ORR) according to the International Myeloma Working Group (IMWG) Response Criteria (Kumar, et al., 2016)
 

Secondary	
To further evaluate the clinical measures of efficacy of belantamab mafodotin and aOX40 in participants with RRMM	Rates of: 
 
Partial Response (PR);
 
Very Good Partial Response (VGPR);
 
Complete Response (CR);
 
Stringent Complete Response (sCR)
 

To describe the exposure of belantamab mafodotin when administered in combination with aOX40 in participants with RRMM	
 
Belantamab mafodotin observed concentration
 

To describe the exposure of aOX40 when administered in combination with belantamab mafodotin.	
 
Combination of belantamab mafodotin with aOX40 treatment's observed concentration.
 

To assess anti-drug antibodies (ADAs) against belantamab mafodotin and against combination treatments (biologics) that are administered by IV infusion.	
 
Incidence and titers of ADAs against belantamab mafodotin and its combination with aOX40, when measured.
 

To further determine the safety and tolerability of belantamab mafodotin in combination with aOX40	
 
AEs of special interest for belantamab mafodotin
 
AEs of special interest for belantamab mafodotin in combination with aOX40
 
Ocular findings on ophthalmic exam
 

### 1.3. Study Design

Overview of Study Design and Key Features													
Please refer to the 208887 Master SAP for overall Study Design for the study													
Design Features	
 
Refer to the 208887 Master SAP for the key design feature for the study
 
												
Dosing	
 
The Starting Dose (SD) for belantamab mafodotin in study 208887 will be 1.9 mg/kg Q3W in combination with aOX40
 
GSK'998 (aOX40) will initially be administered at a flat dose of 8 mg IV Q3W on Day 1 of each 21-day cycle after the infusion with belantamab mafodotin.
 
 
  
 Dose level	Belantamab mafodotin dose	GSK'998 (aOX40) dose	
   
 1 (starting dose level)	1.9 mg/kg	8 mg	
 
 2	2.5 mg/kg	8 mg	
 
 3	2.5 mg/kg	24 mg	
  
 
Note: Dose level 3 was not initiated in this sub-study due to the study being terminated early in the DE phase.
	Dose level	Belantamab mafodotin dose	GSK'998 (aOX40) dose	1 (starting dose level)	1.9 mg/kg	8 mg	2	2.5 mg/kg	8 mg	3	2.5 mg/kg	24 mg
Dose level	Belantamab mafodotin dose	GSK'998 (aOX40) dose											
1 (starting dose level)	1.9 mg/kg	8 mg											
2	2.5 mg/kg	8 mg											
3	2.5 mg/kg	24 mg											
Time & Events	
 
Refer to Section 1.3: Schedule of Activities (SoA) in Sub-study 1 modular protocol
 
												
Treatment Assignment	
 
In DE phase, treatments will be assigned to participants with predefined algorithm.
 
												
Interim Analysis	
 
The Interim Analysis (IA) planned in the DE will not be carried out.
 
												
Blinding	
 
This is an open label study.
 
In DE phase, participants will be assigned to available treatment slots by a predetermined algorithmic approach.
 
												

## 2. STATISTICAL HYPOTHESES

In the DE Phase, the primary objective is to determine the safety and tolerability of belantamab mafodotin and aOX40. No formal statistical hypothesis will be tested.

### 2.1. Multiplicity Adjustment

Analyses of any efficacy endpoints will not be subject to any multiplicity adjustment since each sub-study is analysed separately.

### 3. ANALYSIS SETS

Refer to the 208887 Master SAP Section 3 for the complete list of analysis sets for this study.

### 4. STATISTICAL ANALYSES

#### 4.1. General Considerations

##### 4.1.1. Final Analysis

GSK decided that no further enrolment will take place on this sub-study. As a result, all analyses corresponding to the CE phase, as well as the exploratory endpoints for both the DE and CE phase will not be performed.

The final analyses will be performed after all required database cleaning activities have been completed on available DE data and final database release (DBR) and database freeze (DBF) has been declared by Data Management.

##### 4.1.2. General Methodology

Confidence intervals will use 95% confidence levels unless otherwise specified.

Unless otherwise specified, continuous data will be summarized using descriptive statistics: n, mean, standard deviation (std), median, minimum and maximum. Categorical data will be summarized as the number and percentage of participants in each category.

##### 4.1.2.1. Study Treatment & Sub-group Display Descriptors

Phase	Description
DE	1.9mg/kg GSK916+8mg aOX40
	2.5mg/kg GSK916+8mg aOX40
	2.5mg/kg GSK916+24mg aOX40 

 Note that this dose level was not used due to early termination

##### 4.1.3. Baseline Definition

Refer to the Master SAP section 4.1.4 for details on baseline definitions.

##### 4.1.4. Examination of Covariates, Other Strata and Subgroups

As this sub-study was terminated during the DE phase, covariates, other strata, and subgroups are not applicable as these would have been used in the CE phase only.

### 4.2. Primary Endpoint(s) Analyses

Primary analysis for the DE phase involves summaries of the number and percentages of participants with DLTs and AEs. Both DLTs and AEs will be summarised and listed. All analyses for the DE phase will be based on the Safety population, unless otherwise specified.

### **4.3. Secondary Endpoint(s) Analyses**

Due to this sub-study being terminated early during the DE phase, there will be no primary efficacy analysis for the CE phase as these data were not collected.

#### **4.3.1. Key Secondary Endpoint**

For the definition of the key secondary endpoint, ORR, along with the derivation of confirmed response table please refer to Section 4.2.2.1 of the MSAP.

A summary of investigator assessed best response with confirmation will be produced, using the Safety population.

#### **4.3.2. Secondary Endpoints**

Best Overall Response (BOR) rates (i.e Partial Response (PR) rate, Very Good Partial Response (VGPR) rate, Complete Response (CR) rate and Stringent Complete Response (sCR) rate) will be reported within the summary table described in Section 4.3.1.

The derivation of confirmed response table in Section 4.2.2.1 of the MSAP, will be used confirm the secondary endpoints.

BOR and corresponding response rates will be summarized using descriptive statistics and listed. The corresponding 95% exact CI will also be provided. Participants with unknown or missing responses will be treated as non-responders, i.e., these participants will be included in the denominator when calculating percentages of response.

Other secondary endpoints, PK, ADAs, and AESIs can be found in the sections below.

### **4.4. Exploratory Endpoints Analyses**

Analysis of exploratory endpoints will be performed for neither the DE nor the CE phase, due to the early termination of aOX40.

### **4.5. Safety Analyses**

The safety analyses will be based on the Safety population, unless otherwise specified. Similarly, unless otherwise specified, on-treatment AE's will be reported.

#### **4.5.1. Extent of Exposure**

Refer to the Master SAP Section 4.5.1 for details on the extent of exposure for this study. The cycle length term Q3W is equivalent to a cycle length in days of 21 days, to be used in calculations for treatment exposure.

Extent of exposure to belantamab mafodotin monotherapy and combination therapy will be summarized. For the combination therapy, extent of exposure will be summarized.

A 'by participant' summary listing of data on exposure to all study treatments will be produced.

Dose reductions will be summarised by number of reduction and reasons for reductions. Dose delays/interruptions will be summarised by number of delays, and delay duration (days). All the dose reductions and dose delays/interruptions will be listed.

#### **4.5.2. Adverse Events**

Summaries of all AEs, all drug-related AEs, common non-SAEs, SAEs, and AEs leading to permanent discontinuation of study treatment will be reported by system organ class, preferred term and maximum grade.

Listings of all AEs, fatal SAEs, non-fatal SAEs, reasons for considering as a SAE and AEs leading to permanent discontinuation will be reported.

Dose limiting toxicities (DLTs) will also be summarised and listed.

##### **4.5.2.1. Adverse Events of Special Interest**

The list of terms and reporting requirements for GSK AESI, and the known list of AESIs for GSK'998 can be found in section 8.3.10 of the Sub-Study 1 protocol.

A summary of corneal events by grade will be provided using the GSK scale for all those participants who has an event under protocol amendment 1; using CTCAE scale for all those participants who had an event under protocol amendment 2, and using KVA scale for those patients who had an event under protocol amendment 4. Corresponding listings for ocular events will also be reported, along with a listing of visual acuity by grade.

The grading scales for the GSK and KVA scale for corneal events can be found in Table 6 and Table 7 in the MSAP respectively. For guidance of grading based on changes in visual acuity refer to Table 8 in the MSAP.

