1.1 Synopsis	Added language to state that Sub-study 1 has been closed to enrollment	Due to current data (observed lack of efficacy); investigators and sites have already been notified
Changes in Assessments and SoAs		
1.3 Schedule of Activities	Clarified FISH assessments that are to be completed at Screening (Table 2) based on availability on previous results	In line with other protocols in the program.
	Clarified footnote on Single ECG at Screening (Table 3)	Clarified based on prior edits (Protocol Amendment 03)
	Clarified language on definition of resolution of ophthalmic findings (to baseline instead of Grade 1)	To align with GSK belantamab mafodotin program language
Protocol Clarification and Alignment		
Section 12.11. Appendix 11: Home Healthcare and Telemedicine Approaches	Heading added for this Appendix	Added to match new Appendix added to the 208887 Master Protocol
Editing, format, style changes		
Throughout	Correction of typos and technical document aspects	Minor changes with no impact on content

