### Protocol Amendment 3 (08-JUL-2020)

#### Germany Participation

Sub-study 1 is not applicable for Germany at this time and centers in Germany will not participate in Sub-study 1.

### Protocol Amendment 3 Summary of Changes Specific to Sub-study 1

The protocol has been amended to introduce a new sub-study into Section 14 of the protocol. In addition, changes were made in line with comments from regulators, program level changes and safety updates, which include the following:

- Removal of post-baseline ECG assessments
- Modifications to the Dose Escalation Plan (DEP)
- Revised guidance added for belantamab mafodotin overdose
- Revisions to statistical projections and analyses due to addition of Sub-study 4
- Replaced asset number or abbreviations with generic name belantamab mafodotin
- Included reference Lonial, 2020 to support 2.5 mg/kg starting dose and removal of references to 3.4 mg/kg dose
- Guidance on dose modifications modified to include/change management of IRRs, urine dipstick results, thrombocytopenia, neutropenia without fever, pneumonitis
- Modified text on Risk Assessment for thrombocytopenia, potential cardiotoxicity, immunosuppression
- Minor editorial and document formatting revisions

Section # and Name	Description of Change	Brief Rationale
Revised Study Design		
Section 11.6	Change from 4 to 3 dose levels	See Lonial, 2020 reference for monotherapy recommended dose
Section 11.12.1	Added exclusion for recent symptomatic pericarditis	To better define appropriate study population
Safety Changes		
Section 11.8.2	Change dose reduction table	As above, see Lonial, 2020 reference for monotherapy recommended dose.
Section 11.8.4	Added section on aOX40 overdose	To provide available guidance on overdose
Changes in Assessments and SoAs		
Section 11.2	Specified follow-up ADA assessment for aOX40	Clarified immunogenicity assessments

Section # and Name	Description of Change	Brief Rationale
Section 11.2	Revised assessments and descriptions, including: Urinalysis assessment and description Removal of post-baseline ECG assessments, NT-proBNP, troponin Description of MRI, CT, PET/CT scans for disease assessment in Germany	Provide clarifications and more specific guidance, as with Master Protocol
Section 11.2	Added optional follow-up Qualitative phone interview	Clarified timepoint assessment for qualitative phone interview
Protocol Clarification and Alignment		

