Section 11.2	Replace ophthalmologist and optometrist with eye-care specialist term and define same	Simplify and define provider terminology
Section 11.2,	Revisions to QoL assessments to include IL52 (symptom assessment) portion of EORTC QLQ-My20 and revise timepoints	Clarify assessments and timing Updated QoL assessment reflects disease symptom portion of
Throughout	Asset numbers/abbreviations replaced with generic names except for laboratory sampling	For consistency throughout document
Editing, format, style changes		
Throughout	Correction of typos and technical document aspects	Minor changes with no impact on content

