## Protocol Amendment 2 (16-DEC-2019)

### Protocol Amendment 2 Summary of Changes Specific to Sub-study 1

Section # and Name	Description of Change	Brief Rationale
Revised Study Design		
Section 11.2, 11.13.1	Updated pregnancy wording: follow up timing and management of pregnancy.	Program level changes
Safety Changes		
Section 11.2	Ophthalmology wording updated throughout the protocol. Changes in the frequency of assessments. The GSK scale removed, steroid eye drops not mandatory and corneal images no longer required. Updated stopping criteria based on ocular examination findings	Updated in line with program level changes.
Section 11.2 SoA tables	Updated timing of SAE assessments.	Updated timing of SAE assessments in line with program.
Changes in Assessments and SoAs		
Section 11.2, Table 21, Table 22	CRP assessment removed from SoA tables	
Section 11.2	Removed physical exam and vital sign assessment from SoA table of assessments to be done regardless of dosing (and updated footnote numbering)	These evaluations are done with dosing
Section 11.2, Table 23 and 24	Removed AESI assessment.	This is covered under AE's and SAEs. This is still being collected.

Section # and Name	Description of Change	Brief Rationale
Section 11.2, Table 23	Clarification around timings for biomarker samples.	Clarifications
Protocol Clarification and Alignment		
Section 11.6	Added wording that "Sponsor may decide not to evaluate all dose levels based on data external to this study..."	Clarity of wording around when a sub-study can be closed
Section 11.7, Table 26	Infusion timing of belantamab mafodotin and GSK'998 (OX40) added	Regulatory Agency request. Infusion timings added
Section 11.4	Rationale for combination of belantamab mafodotin with GSK'998 (aOX40) preclinical wording clarified	Regulatory Agency request for clarified wording
Section 11.13	Clarification around wording for the administration of GSK'998 only to be administered with GSK'916 with the possibility of GSK'998 administration 1 day later than GSK'916 in the case of an IRR on the date of GSK'916 infusion and the maximum treatment delay for GSK'998.	Regulatory Agency request for clarified wording

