#### **4.5.3. Other Safety Assessments**

The analyses of non-laboratory safety test results including ECGs and vital signs will be based on GSK Core Data Standards, unless otherwise specified. LVEF and Performance status will be summarized and listed based on GSK Oncology Data Standard. The details of the planned

displays are presented in the OPS document. For more detail please refer to Section 4.5.3 of the Master SAP.

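### Does it matter that the SAP names a corneal grading scale for protocol amendments 1, 2 and 4 only?

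*SAP*

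**What the plan says.** SAP 4.5.2.1 (Adverse Events of Special Interest) ties the graded corneal summary to protocol versions. Events under amendment 1 use the GSK scale. CTCAE is for participants who "had an event under protocol amendment 2, and using KVA scale for those patients who had an event under protocol amendment 4". The same section promises listings of ocular events and of visual acuity by grade, and sends the reader elsewhere for definitions: "The grading scales for the GSK and KVA scale for corneal events can be found in Table 6 and Table 7 in the MSAP".

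The protocol's change logs give partial background:

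- Amendment 2 (16-DEC-2019): "The GSK scale removed, steroid eye drops not mandatory and corneal images no longer required". The replacement scale is not named.
- Amendment 3 (08-JUL-2020): the eye-related entry is "Replace ophthalmologist and optometrist with eye-care specialist term and define same", and the dose-guidance item reads "Guidance on dose modifications modified to include/change management of IRRs, urine dipstick results, thrombocytopenia, neutropenia without fever, pneumonitis". Neither mentions corneal grading.
- Amendment 4 (14-DEC-2020): the ophthalmic entry is "Clarified language on definition of resolution of ophthalmic findings (to baseline instead of Grade 1". KVA does not appear.

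The SAP version history bases the plan on amendment 5 (21-JAN-2022). SAP 1.2, Table 2, lists belantamab mafodotin AESIs and ophthalmic exam findings as secondary safety endpoints. SAP 4.5.2 adds summaries of all AEs that "will be reported by system organ class, preferred term and maximum grade". For other safety outputs, SAP 4.5.3 notes that the planned "displays are presented in the OPS document".

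**The concern.** The rule skips a version that mattered. Amendment 3 sits between two amendments that do have a scale, and by document date it was in force when the sponsor closed the sub-study. Protocol Table 3 schedules eye exams every three weeks up to the sixth belantamab mafodotin dose, so corneal findings in that period are plausible.

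A programmer who took the sentence literally would have no scale for an amendment 3 event and might leave it out of the graded summary. With nine participants, one missing person is visible. The original protocol and amendment 5 are also unassigned, and nothing says how to count a participant with events under two versions. At stake is the completeness of one table supporting a secondary safety endpoint.

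**Working it through.** The SAP states no figure to reproduce. The check compares the protocol versions with the scales named, and uses date arithmetic to see how long each version was current. Dates come from the protocol's document history and the SAP version history. Document dates stand in for site implementation dates, which are not given.

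| Version | Date | Days until next version | Scale in SAP 4.5.2.1 |
|---|---|---|---|
| Original | 12-MAR-2019 | 104 | none |
| Amendment 1 | 24-JUN-2019 | 175 | GSK |
| Amendment 2 | 16-DEC-2019 | 205 | CTCAE |
| Amendment 3 | 08-JUL-2020 | 159 | none |
| Amendment 4 | 14-DEC-2020 | 403 | KVA |
| Amendment 5 | 21-JAN-2022 | not applicable | none |

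**Extent of the gap.** Three of five amendments, or three of six versions, have a scale. Up to amendment 5 the total is 104 + 175 + 205 + 159 + 403 = 1046 days. The unassigned part is 104 + 159 = 263 days, and 263 / 1046 = 25%. This is calendar time, not a share of events.

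**Position of the closure.** The SAP gives only October 2020. From 08-JUL-2020 to 1 and 31 October is 85 and 115 days. From those dates to 14-DEC-2020 is 74 and 44 days. Amendment 3 was therefore current by document date at closure.

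**Can the missing scale be inferred?** Only weakly. The GSK scale went at amendment 2, the SAP ties KVA to amendment 4, and the Sub-study 1 log for amendment 3 shows no grading change. That leaves CTCAE by elimination. But the log covers only changes specific to Sub-study 1, and the amendment 4 log does not record KVA, although the SAP attaches KVA to that amendment. If the logs can miss one change of scale, their silence about amendment 3 proves little.

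**Is the amendment 5 gap empty?** It is dated 447 days (from 31-OCT-2020) to 477 days (from 01-OCT-2020) after closure. That does not settle the matter. Protocol 1.1 and SAP 4.1.1 describe closure to enrolment. Protocol 6.2 lets treatment run until progression or another listed stopping event, and Table 5 allows eye follow-up for up to 12 months after treatment. Events under amendment 5 cannot be ruled out.

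**What would be lost on a literal reading?** One graded summary could miss events. The all-AE summaries by maximum grade (SAP 4.5.2) and the ocular listings (SAP 4.5.2.1) state no amendment limit, so the events would still be reported, though not necessarily by corneal-scale grade in a summary table. SAP 2 plans no hypothesis test, and no conclusion rests on this table.

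**The case for a change.** The strongest case for a change is that it costs almost nothing and the gap is real. One clause would do, in a section on a known toxicity of the drug. The SAP assigns a scale to amendment 4, dated after the closure decision, so it expects corneal events that late, and closure cannot explain skipping the version before it. The section cites the Master SAP for the content of the scales, not for which amendment uses which. Leaving the scale open also means it could be settled after open-label data are known.

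The textual gap stands, and it extends to the original protocol, amendment 5 and participants with events under several versions. The rest carries less weight. The scale on which a grade was recorded was fixed at data capture, so the analyst's task is to report it, not choose it. Settling details late is not particular to this point, because the whole SAP rests on a protocol version dated after closure. The wording that suggests itself (CTCAE for amendments 2 and 3, KVA from amendment 4 onwards) cannot be confirmed from these documents. The most one could ask is that the sponsor write down which scale was used, and that request alters no analysis.

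**Conclusion.** No change is needed. SAP 4.5.2.1 leaves three of six protocol versions without a named corneal grading scale, and these documents do not establish which scale applied under them. This is an unwritten detail that analysts would fill sensibly by reporting each event on its recorded scale. It affects one descriptive table in nine participants, and the events remain visible in other planned outputs. No effect on any estimate or conclusion is shown.

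This rests on three assumptions: that the scale used for each event can be recovered from the study data, that document dates roughly track the versions in use at sites, and that neither the Master SAP nor the OPS document contradicts the sensible reading. Either of those two documents may already give the rule. Corneal event counts under the unassigned versions are not given. If there were none, the question has no practical content. If the sponsor revises the SAP for another reason, naming the scale for each version would be a courtesy to the reader.
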